4.3.2 Provider Schedule of Events

Figure 3: Timeline of events for providers.

We anticipate that providers study participation will be approximately 11 months in duration. All providers at The Late Effects Clinic will be invited to view an online training on how to use the PREVENT tool prior to the start of patient recruitment. The online training will be recorded and disseminated to ensure that all providers are able to view the training. At this time, providers will be supplied login credentials to access the PREVENT tool. Following the training, all providers will be asked to complete the Clinical Sustainability Assessment Tool electronically. Once the intervention period begins, study staff will notify the provider if their patient was randomized to intervention to ensure that PREVENT is used during the care visit. Tablets will be available at the clinic if providers choose to use them to administer the PREVENT tool. However, the PREVENT tool can be administered via any computer or tablet using their login credentials. A subset of patient-provider interactions (n=15) may be observed and recorded while PREVENT is being used. Providers who used PREVENT will be asked to complete an electronic follow-up survey. Within one month of completing the intervention, providers will participate in in-depth interviews. Interviews will be held in-person, over the phone or using zoom technology.

FOR IRB USE ONLY \$STAMP_IRB_ID \$STAMP_APPRV_DT \$STAMP_REL_DT \$STAMP_EXP_DT

4.4 Data Collection Methods

Theoretical underpinnings. This feasibility study will apply principles of Designing for Dissemination, Implementation and Sustainability (D4DIS) to understand factors critical to external validity and refine the existing PREVENT tool to fit well with provider's and patient's needs, assets and timeframes.³⁹ We seek to speed translation of the PREVENT tool into practice by simultaneously collecting mixed method data regarding determinants of current and future implementation of the PREVENT tool, guided by the new Reach, Efficacy, Adoption, Implementation, and Maintenance (RE-AIM) framework.^{40,41} The updated RE-AIM framework will be used to identify barriers to implementation and dissemination as outlined in **Table 3**.

RE-AIM Construct	Measure	Data Source	Stakeholder
Reach	Representativeness compared to eligible clinic population	EHR data; Demographics survey	Patients
Efficacy	Changes in health behaviors and attitudes; Change in CVH risk factors	Health Behavior & Attitudes Survey; accelerometry; EHR data	Patients
Adoption	Usability; acceptability; consistency with priorities/values	Patient and parent interviews; Provider survey	Patient, parent, provider
Implementation	Intervention delivery; fidelity to the protocol; time of PREVENT use; compatibility with workflow	Direct observation, audio recordings of implementation	Patient
Maintenance	Barriers and enabling factors for continued implementation of PREVENT	Qualitative interviews; Provider survey; Clinical Sustainability Assessment Tool	Provider

Table 3: RE-AIM Outcome Measures

4.4.1 EHR data extraction. Patient demographics (e.g., sex, date of birth, race/ethnicity) and the most recent risk factors for CVH (height, weight, fasting blood glucose, total cholesterol, blood pressure, smoking status) will be extracted at baseline (prior to clinic visit) and at follow-up (3-months). Available EHR data will be uploaded into PREVENT prior to the clinic visit but may be updated within the PREVENT tool at the time of the clinic visit if updated values are attained. CVH risk factor data within the tool at the time of the clinic will be used as baseline values and used to determine changes from baseline to follow-up. Only patients with abnormal baseline values will return for a follow-up clinic visit at 3-months. Therefore, we acknowledge that not all patients will have updated

FOR IRB USE ONLY \$STAMP_IRB_ID \$STAMP_APPRV_DT \$STAMP_REL_DT \$STAMP_EXP_DT

information for CVH risk factors (BMI, fasting blood glucose, total cholesterol and blood pressure) from baseline). This feasibility study is intended to determine what data are commonly available for a future study. We expect that height and weight will be the most commonly available data point at baseline and 3-months. Therefore, body mass index (BMI) is our primary health outcome and will be calculated based on CDC growth charts using height and weight.

4.4.2 Demographics Survey will be used to collect parent and family demographics (e.g. annual household income, education-levels, family's medical history) from parents of study participants (n=50) at baseline. The survey will be sent electronically using REDCap to give the parent the option of completing the survey prior to the clinic visit. Alternatively, the parent may complete the questionnaire while in the waiting room at the clinic.

4.4.3. Health Behavior & Attitudes Survey will be used to collect physical activity and nutrition behaviors and attitudes from adolescent patients (n=50) at baseline and follow-up. This information will be used to populate the PREVENT tool's risk profile and determine changes in physical activity and nutrition behaviors and attitudes from baseline to post-intervention. The physical activity questions are adapted from the International Physical Activity Questionnaire (IPAQ) that has been validated for use in adolescents.^{42,43} Nutrition questions are generated based on the Stoplight Diet³⁸ for adolescents and the Rapid Eating Assessment for Participants - Shortened Version.⁴⁴ Attitudes toward behavior change questions were adapted from two validated surveys: 1) ⁴⁵⁻⁴⁷the Treatment Self-Regulation Scale ^{48,49} and 2) the Rapid Eating Assessment for Participants - Shortened Version.⁴⁴

4.4.4 Accelerometers will be administered to patients at baseline and 6-month follow-up to objectively measure levels of physical activity (light, moderate, vigorous) and sedentary behaviors. At baseline, accelerometers will be mailed to participants after consent is obtained and returned by mail using a provided prepaid envelop or at the clinic visit. The following materials will be sent via mail with the accelerometer device: a pre-paid return envelope, a welcome letter, and directions for use. Participants randomized to the intervention group will also receive a document detailing "what to expect" at their clinic visit. At follow-up, accelerometers will be mailed including a pre-paid return envelope. Participants will be asked to wear the device for 7 days including 2 weekend days on a belt (provided) around their waist. Participants will be instructed to remove the device only when bathing or swimming; they will continue to wear the device while sleeping.

4.4.5 Patient and parent qualitative interviews will examine facilitators and barriers to *maintenance*. Semi-structured interviews will be conducted individually with patients (n=10) and parents (n=10). Questions will assess satisfaction with their provider interaction, the PREVENT tool's design, physical activity and nutrition prescriptions, community resources (*e.g.*, are there other resources that would be helpful, did these resources help you or your child achieve the goals)

FOR IRB USE ONLY \$STAMP_IRB_ID \$STAMP_APPRV_DT \$STAMP_REL_DT \$STAMP_EXP_DT

and, more generally, other ways the clinic may help them achieve behavior change.

4.4.6 Provider survey will be conducted following the intervention to evaluate *adoption* and understand potential for *maintenance*. All providers will complete a web-based survey adapted from five previous instruments. The acceptability, appropriateness, and feasibility of the PREVENT tool will be assessed using the Acceptability of Intervention Measure (AIM), Intervention Appropriateness Measure (IAM), and Feasibility of Intervention Measure (FIM).⁴⁴ Questions regarding the provider's satisfaction with five aspects of health information technology: content, accuracy, format, ease of use and timeliness are adapted from [name] (Co-I) previous research.³⁴ Question to assess providers intent to change their behavior and continue using PREVENT (maintenance) were adapted from Legare's CPD Reaction Questionnaire.⁵⁰⁻⁵² We also include several team-developed items to align with previous measurement in the tool development phase.

4.4.7 Direct observation, audio recordings of 15 patient-provider interactions will generate the following *implementation* outcomes: the delivery of the PREVENT tool (*e.g.*, who is delivering the tool, how the provider delivers the information), whether it was delivered as intended (fidelity) and compatibility with clinic workflow. Additionally, observation will provide information on how the patient interacts with the tool. An observation form will be used by study staff to systematically observe PREVENT use. Audio recording will occur only while PREVENT is being used and will be assessed by two study staff to identify themes in patient-provider interaction and clinical decision-making.

4.4.8 Patient follow-up surveys will be sent electronically at 4-, 8- and 12weeks to assess whether patient's are obtaining their physical activity and food intake goals and provide tailored feedback (e.g., updated goals and motivation).

4.4.9 Provider qualitative interviews will be conducted following the 4-month period to understand potential for *maintenance*. Thirty-minute interviews will be performed with a diverse group of 5-10 providers (*e.g.,* physicians, physician assistants, nurses, clinic staff) at the clinic, by phone or by zoom technology. Interviews will be used to gain in-depth insight on what providers liked about the PREVENT tool, whether PREVENT is consistent with their and their clinic's priorities/values, and barriers and enabling factors for sustaining PREVENT in their clinic.

4.4.10 Clinical Sustainability Assessment Tool (CSAT) will be administered to all providers at the Late Effects Clinic following the intervention. CSAT will be administered to determine clinic-level readiness and capacity for sustainability of the PREVENT tool.⁵³ Clinic-level factors include organization, financial, regulatory and political barriers.

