4.3 Schedule of Events

4.3.1 Patient Schedule of Events

We anticipate that study participation will be between 4 and 5 months from the point of recruitment to completion (Figure 2).

Figure 2: Timeline of events for an enrolled patient.

Consent, enrollment & baseline measurement will occur electronically or via mail prior to the clinic visit. The patient will complete a written signed consent,

FOR IRB USE ONLY \$STAMP_IRB_ID \$STAMP_APPRV_DT \$STAMP_REL_DT \$STAMP_EXP_DT

complete a survey assessing their health behaviors and attitudes and wear an accelerometry device for 7 days prior to the clinic visit. Parents/legal guardians of study participants will be asked to complete a baseline demographics survey delivered electronically before the clinic visit or completed in the waiting room at the clinic visit. In addition, study staff will extract EHR data (patient demographics and CVH risk factors) and upload the most recent information into the PREVENT tool prior to the patient's clinic visit. The patient will be randomized to intervention or wait-list control.

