PREVENT tool interaction (intervention). The patient will attend a routine clinic visit remotely or in-person at the Late Effects Clinic at either St. Louis Children's Hospital or the St. Louis Children's Specialty Care Center. During this visit, the provider will use PREVENT on a tablet or computer (in-person or via a teleconference call) to discuss risk, and deliver a tailored behavior change plan inclusive of patient-centered community resources. The PREVENT tool will be pre-loaded by study staff with all necessary patient information (demographics and CVH risk factors) and show the date in which these data were collected. The provider may update any patient information at the time of the visit. PREVENT uses a robust informatics approach developed by [name] (secondarymentor)³⁴⁻³⁶ to visually display Life's Simple 7 Cardiovascular Risk Factors (e.g., weight, blood pressure, inactivity) and calculate the patient's overall risk for developing cardiovascular disease. Physical activity and food intake recommendations that are tailored to the patient's current weight status and health behaviors using evidence-based recommendations (Trim Kids,³⁷ the Stoplight Diet³⁸) proven to be effective in youth are delivered to the patient. An interactive map of community resources near the patient's home will allow the patient to select resources that will support the recommended behavior change. Community resources (e.g., parks, fitness and recreation centers, farmer's markets, food pantries) were pulled from YELP using an API key. Resources were validated against lists manually generated via online searching of physical activity and food departments and organizations (e.g., the department of parks, recreation and forestry) and google. A final action plan (behavior change prescription, community resources and education) will be provided to the patient at the visit and/or electronically via email or text-message. Patient follow-up will be supported by automatic email or text-message check-ins at 4, 8 and 12 weeks. Within the 4-, 8- and 12- week email/text message check-ins the patient will be asked to answer questions about meeting their physical activity and nutrition goals. Based on the response, the patient will receive an automated email and/or text message with an updated prescription.

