Wait-list control. Patients will attend a routine care visit in-person or remotely. A PREVENT action plan (behavior change prescription, community resources and education) will provided to the patient via email after the completion of follow-up measurement.

Follow-up measurement. Immediately following the clinic visit (within 48 hours) all patients will be sent electronically a brief 10-question (yes/no) survey regarding their clinical interaction. Participants randomized to intervention will also receive questions about their satisfaction with the

FOR IRB USE ONLY \$STAMP_IRB_ID \$STAMP_APPRV_DT \$STAMP_REL_DT \$STAMP_EXP_DT

PREVENT tool. Three months after the patient's clinic visit, they will be sent the Health Behavior & Attitudes Survey electronically and an accelerometer via mail. Only patients who presented with abnormal values for CVH risk factors will return to the Late Effects Clinic to complete a routine clinic visit in accordance with the standard of care for these high-risk patients. Study staff will extract the most-recent EHR data for CVH risk factors for all patients.

Qualitative data collection. Semi-structured interviews will be completed within one month of the completion of follow-up measurement for all participants that received the PREVENT tool.

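### Baseline BMI and other CVH values are read from the PREVENT tool at the visit, after randomisation, and the only described route to a visit-day value runs through the intervention arm

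*Combined protocol and SAP*

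**What the plan says.** All references are to the combined protocol and SAP.

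- **Order of events (4.2.1).** Patients complete the questionnaires and accelerometry, are randomised, and then attend the clinic visit.
- **Pre-load (4.3.1).** Staff extract EHR data and "upload the most recent information into the PREVENT tool prior to the patient's clinic visit". No arm is named and no maximum age of a value is set.
- **Update, general rule (4.4.1).** The loaded values "may be updated within the PREVENT tool at the time of the clinic visit if updated values are attained". Again no arm is named.
- **Update, who does it (4.3.1, intervention paragraph).** "The provider may update any patient information at the time of the visit".
- **Who is prompted to use the tool (4.3.2).** "study staff will notify the provider if their patient was randomized to intervention to ensure that PREVENT is used during the care visit".
- **Control visit (4.3.1, wait-list paragraph).** "Patients will attend a routine care visit in-person or remotely". No use or update of the tool is described. The action plan is emailed once follow-up measurement is complete.
- **Baseline definition (4.4.1).** "CVH risk factor data within the tool at the time of the clinic will be used as baseline values and used to determine changes from" that starting point.
- **Follow-up (4.3.1).** "Study staff will extract the most-recent EHR data for CVH risk factors for all patients". Only patients with abnormal values return at 3 months.
- **Analysis (4.4.1, 5.2).** BMI is the primary health outcome. Change from baseline is compared between groups by linear regression at p<0.05, with no term named for the source or date of the baseline value.

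**The concern.** A baseline should be obtained in the same way in both arms, and preferably before allocation can influence it. Here the value that counts is fixed after allocation. The one mechanism described for refreshing it is part of delivering the intervention. Where a provider enters that day's height and weight, the intervention patient's change starts at the visit. A control whose record is not refreshed starts from an EHR value of unknown age, possibly the same value that met the entry rule of BMI at or above the 85th percentile.

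Two distortions follow, and they pull in opposite directions:

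- If BMI was rising before the visit, the control's change includes that extra rise, which favours PREVENT.
- If the older value was high partly because patients were selected on it, the control's change includes a fall back towards the mean that an updated intervention baseline has already undergone. This works against PREVENT.

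Randomisation does not balance a difference in measurement that arises after it, and a larger sample would not remove it. Blood pressure, cholesterol and glucose are exposed in the same way.

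**Working it through.** The plan gives no figure to reproduce: the sample of 50 comes with no power, effect size or standard deviation. The structural point rests on the text. The arithmetic only shows how large the effect could be.

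**1. Which value counts as baseline**

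| Patient | Tool content at the visit | Baseline under 4.4.1 |
|---|---|---|
| Intervention, new value obtained and entered | visit-day value | visit-day value |
| Intervention, no new value or not entered | pre-loaded EHR value | older value |
| Control, visit as described | pre-loaded EHR value | older value |

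The first row has no described counterpart among controls.

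**2. A patient who does not return.** Let A be the pre-loaded value and B the index-visit value, with B recorded in the EHR and nothing later. The follow-up rule picks B. For a control, change = B − A, which is purely pre-visit change. For an updated intervention patient, change = B − B = 0. An apparent contrast can arise with no data from after the visit.

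**3. Drift in raw BMI.** Let g be the annual drift, L the record age in months, and uI and uC the shares updated in the intervention and control arms.

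Spurious difference = g × (L/12) × (uI − uC)

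Assumptions, none from the documents: g = 0.5 to 1.0 kg/m² per year, L = 3 to 12 months, uC = 0, uI = 50 to 100%.

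- Low end: 0.5 × 3/12 × 0.5 = 0.0625, about 0.06 kg/m².
- Middle: 0.5 × 6/12 × 1.0 = 0.25 kg/m²; 1.0 × 6/12 × 1.0 = 0.50 kg/m².
- High end: 1.0 × 12/12 × 1.0 = 1.0 kg/m².
- uI = uC: 0.

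**4. Effect on the test.** Further assumptions: 25 per arm, all with both values; a two-sided 5% test; SD of change 0.8 or 1.2 kg/m². The standard error is SD × √(2/25), that is 0.226 or 0.339. With b the spurious difference, the chance of p<0.05 with no true effect is Φ(b/SE − 1.96) + Φ(−b/SE − 1.96).

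| b (kg/m²) | SD 0.8 | SD 1.2 |
|---|---|---|
| 0 | 0.05 | 0.05 |
| 0.06 | 0.06 | 0.05 |
| 0.25 | 0.20 | 0.11 |
| 0.50 | 0.60 | 0.31 |
| 1.0 | 0.99 | 0.84 |

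**5. Regression to the mean on the z-score.** Assume standard normal z-scores selected on the stored value at the 85th percentile (z = 1.036). The mean z above the cut is φ(1.036)/0.15 = 1.554. With correlation r between the stored and visit-day z-scores, the expected fall is 1.554 × (1 − r): 0.031 at r = 0.98, 0.078 at 0.95, 0.155 at 0.90. Multiplying by an update-share difference of 0.5 to 1.0 gives 0.016 to 0.155 z, against PREVENT.

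Steps 3 and 5 have opposite signs and different scales. They cannot be netted without figures that the documents do not give.

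**The case against.** A reader might infer a clean split, with every intervention baseline taken on the day and every control baseline old. The documents do not support that:

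- Updating is optional and depends on new values being obtained.
- Intervention visits may also be remote ("The patient will attend a routine clinic visit remotely or in-person at the Late Effects Clinic"), so a new height and weight is not assured. An intervention patient who is not updated keeps the older value, just as a control does.
- The general update sentence in 4.4.1 names no arm, all providers receive logins (4.3.2), and nothing forbids entering a control's new values.
- A pre-loaded value may be recent.

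These points stand, and they reduce the bias. They do not secure equal updating, since only intervention use of the tool is prompted.

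The raw-BMI illustration may also be on the wrong scale. Section 2.0 lists BMI z-score, and 4.4.1 refers to CDC growth charts. Age standardisation would absorb part of the drift if age is taken at the measurement date, and the tool displays collection dates (4.3.1). That stands too. It leaves the regression to the mean in step 5, and it does nothing for blood pressure or laboratory values.

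Finally, this is a feasibility study that expects incomplete CVH data, and dated EHR values could be re-extracted before analysis. That makes the problem recoverable. Even so, 5.1 states a comparative hypothesis, 5.2 tests it, and the results are to inform a larger trial.

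**Conclusion.** The concern holds in a limited form. The baseline rule permits an arm-dependent baseline for the primary health outcome and the other CVH values, set after randomisation, and the change analysis does nothing about it. How far this happens depends on record age, the update share in each arm and the BMI scale analysed. The documents do not give the first two, and 5.2 does not say which scale is tested. Under the stated assumptions the spurious raw-BMI difference is about 0.06 to 1.0 kg/m². It is smaller on an age-standardised z-score and zero if update shares are equal.

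A reader might go further and conclude that the bias must favour PREVENT, or that the BMI contrast is certain to be misleading. Neither follows: the two mechanisms oppose each other, and every input to their size is assumed.

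**What to change.** Replace the baseline sentence in 4.4.1 with one rule for both arms:

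- Baseline height, weight, blood pressure and laboratory values are the dated EHR values from the index visit. If none were taken, as may happen with a remote visit, use the last EHR value before the visit within a fixed look-back that is identical in both arms.
- Keep the measurement date, and compute BMI z-score from age on that date.
- Do not take baseline from tool content.
- Count a follow-up value only if it was measured after the index visit. Without this condition, a non-returner's index-visit record could serve as both baseline and follow-up, giving a change of zero.

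With one source in both arms, uI = uC in the formula above and the spurious difference from this cause is zero.

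The cost is protocol wording and one further EHR extraction per patient, with no new visit or measurement. Some patients will have no in-window baseline or follow-up value. Reporting their number by arm would serve the plan's own aim of learning which data are commonly available.

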2.0 Summary of Study Plan

Fifty adolescents aged 12 to 19 years at risk for poor CVH (BMI \geq 85th percentile) will be recruited over a 9-month period (**Table 1**) from the Late Effects Clinic and randomized to intervention or wait-list control (**Figure 1**). Provider's and patient's perceptions of barriers to implementation and maintenance of PREVENT (*e.g.*, usability, acceptability, motivation for use, workflow compatibility) will be

Year	1		2					
Quarter	1	2	3	4	1	2	3	4
Recruit Advisory Board								
Develop Manual of Procedures								
IRB Approval								
Train Study Staff								
Advisory Board Bi-Annually								
Recruit								
PREVENT Feasibility Study								
Data Analysis								
Manuscript Development								
Refine PREVENT Tool								
R01 Submission								

examined using: 1) surveys administered to all providers at clinic; 2) semi-structured interviews with 5-10 diverse providers (*e.g.*, physicians, nurses, clinic staff, clinical research associates); and 3) two focus groups, one with patients (n=10) and one with parents (n=10) (**Aim 1**). These evaluations will be guided by RE-AIM³³ and administered following the intervention period. Implementation (*e.g.*, intervention delivery, fidelity, time

FOR IRB USE ONLY \$STAMP_IRB_ID \$STAMP_APPRV_DT \$STAMP_REL_DT \$STAMP_EXP_DT

of use) will be examined using direct observation and audio recordings of 15 providerpatient interactions while using PREVENT. Patient attitudes toward behavior change recommendations and risk factors (BMI z-score, cholesterol, blood pressure, physical activity and food intake) will be measured using surveys, physical activity tracking devices (accelerometers) and EHR-data extraction at baseline and 3-months (**Aim 2**). An advisory board will be established and meet bi-annually to provide adolescent (n=5), parent (n=5) and provider (n=5) perspectives on study implementation and inform revisions to PREVENT.

Key dates (Table 1).

- Provider training: October 2020-January 2021
- Patient recruitment: February 2021- April 2021
- PREVENT feasibility study: January 2021-September 2021

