measures will be administered immediately following the clinic visit (within 48 hours) and 3-months after the clinic visit electronically and by mail. Patients will only return to the clinic for a routine visit at 3-months if it meets their standard of care based on their baseline clinical values for CVH risk. Wait-list control will be sent tailored prescriptions via the PREVENT tool following the completion of follow-up measurements. Participants will receive up to \$75 dollars in gift cards for participation. Participants will receive \$25 after baseline, \$25 after 3-month follow-up and \$25 for wearing an accelerometry device to measure their physical activity.

Patients (n=10) and their parents (n=10) who participate in focus groups will provide an additional written consent in-person prior to the start of the discussion. Consent will be administered in a single room with patients and parents. Once consent is administered, patients and parents will be divided into two private rooms to conduct separate focus groups simultaneously.

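### Section 4.4.4 places follow-up accelerometry at 6 months, while sections 2.0 and 4.3.1 place it at 3 months and participation is expected to last only 4 to 5 months

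*Combined protocol and SAP*

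**What the plan says.** Section 4.4.4, which holds the working instructions for the device (mailing, wear, return), reads: "Accelerometers will be administered to patients at baseline and 6-month follow-up". It lists those two administrations and no 3-month one.

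The other places that bear on timing are these:

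- Section 2.0 measures Aim 2 outcomes with surveys, "physical activity tracking devices (accelerometers) and EHR-data extraction at baseline and 3-months".
- Section 4.2.1 says that follow-up "measures will be administered immediately following the clinic visit (within 48 hours) and 3-months after the clinic visit electronically and by mail".
- Section 4.3.1, under follow-up measurement: "Three months after the patient's clinic visit, they will be sent the Health Behavior & Attitudes Survey electronically and an accelerometer via mail".
- Section 4.3.1, opening: "We anticipate that study participation will be between 4 and 5 months from the point of recruitment to completion".
- Section 4.4.1 extracts follow-up EHR risk factors at 3 months.
- Sections 4.3.1 and 4.4.8 schedule the last intervention check-in at 12 weeks.
- Section 5.2 tests change from baseline between groups by linear regression and does not say at which time point.

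The key dates in section 2.0 add "Patient recruitment: February 2021- April 2021" and "PREVENT feasibility study: January 2021-September 2021". The same section also says that patients "will be recruited over a 9-month period".

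**The concern.** One measure has two follow-up times in the current text. Table 3 names accelerometry as an efficacy data source, and it is the only device-based measure of activity for Aim 2. Staff running the device mailings would reasonably work from 4.4.4. If they did, the activity outcome would come about three months after the survey and EHR outcomes, and it would not be the baseline-to-3-month change that section 2.0 describes. An analyst could not resolve this from section 5.2.

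A secondary issue is the wait-list arm, which receives PREVENT once follow-up measurement is complete. If staff regarded follow-up as complete at 3 months, controls could be given PREVENT before a 6-month wear, and the device comparison would no longer be against an unexposed group. If release instead waited for the 6-month wear, controls would receive PREVENT about three months later than the rest of the plan implies.

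**Working it through.** The plan gives no calculated figure to reproduce. The check compares the passages and adds up the stated durations.

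**Inputs.** Follow-up wear at 6 months (4.4.4) or 3 months (2.0, 4.3.1). Wear period of 7 days (4.4.4). Baseline wear for 7 days before the visit (4.3.1). Anticipated participation of 4 to 5 months (4.3.1). Recruitment February to April 2021 and feasibility study to September 2021 (2.0, key dates). One month is taken as 365.25/12 = 30.44 days, so 7 days = 0.23 month.

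**Step 1: duration against the anticipated 4 to 5 months.** Consent, mailing, scheduling and interview time are left out, so these are minimum durations.

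| Follow-up wear | Counted from baseline | Counted from visit |
|---|---|---|
| 6 months | 6 + 0.23 = 6.23 | 0.23 + 6 + 0.23 = 6.46 |
| 3 months | 3 + 0.23 = 3.23 | 0.23 + 3 + 0.23 = 3.46 |

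The 6-month excess over the upper end is 6.23 − 5 = 1.23 to 6.46 − 5 = 1.46 months. Even 6 months counted from recruitment, with no wear time added, exceeds 5. The 3-month version leaves between 4 − 3.46 = 0.54 and 5 − 3.23 = 1.77 months for the omitted steps. That is compatible with the stated range but does not prove it.

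**Step 2: gap to the other Aim 2 outcomes.** Six months is 26.09 weeks and three months is 13.04 weeks. Counted from the visit, the gap is 26.09 − 13.04, about 13.0 weeks. Counted from the start of a baseline wear 7 days before the visit, the 6-month point falls 25.09 weeks after the visit, so the gap is about 12.0 weeks. It is shorter if baseline was earlier.

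**Step 3: calendar, under the key dates only.** Assume the fastest path: baseline wear starts on the day of recruitment and the visit is 7 days later.

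- Recruited 30 April 2021, 6-month wear: from baseline, 30 October to 6 November, ending 37 days after 30 September; from the visit, 7 to 14 November, ending 45 days after.
- Same patient, 3-month wear: ends 6 August (55 days before 30 September) or 14 August (47 days before).
- The window from 1 February to 30 April has 28 + 31 + 30 = 89 days. A 6-month wear ends after 30 September for recruits from 24 March (38/89 = 43%, baseline anchor) or from 17 March (45/89 = 51%, visit anchor).

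These are shares of calendar days, not of patients, since no accrual rate is given. Any delay before the visit raises the visit-anchored share, and any delay before baseline raises both.

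**Step 4: could both timings be intended?** An extra 6-month wear on top of a 3-month one does not fit 4.4.4, which lists only baseline and the single follow-up. No other readable text mentions a 6-month patient measure. Figure 2 and the shading of Table 1 could not be read.

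**The case against.** The strongest reply is that this is a single slip whose intended value can be recovered. Section 4.3.1 is explicit about 3 months, section 2.0 agrees, the check-ins end at 12 weeks, and nothing else readable supports 6 months. The primary health outcome is untouched, and activity is also measured by survey. All of that is correct, and it limits the seriousness of the point. It does not remove the conflict, because the wrong figure stands in the section that governs the device.

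Several narrower objections also have force:

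- **The calendar check is supporting evidence only.** Section 2.0 gives both a three-month recruitment window and a 9-month one. If recruitment ran nine months from February 2021, even 3-month follow-up would pass September, and the check would no longer separate the two timings. Nor does the plan define September as the end of patient measurement. Counting a 7-day wear as seven calendar dates moves the overruns to 36 and 44 days and the shares to 37/89 = 42% and 44/89 = 49%, which changes nothing of substance.
- **The wait-list exposure is unlikely.** Section 4.3.1 lists the accelerometer within follow-up measurement, so release should wait for it. Its size cannot be computed, and the conclusion does not depend on it.
- **Some corroboration is indirect.** Section 4.4.1 times EHR extraction rather than the device, section 4.2.1 does not name the device, and section 2.0 does not tie its 3 months to the visit.
- **The 4 to 5 months is an expectation, not a limit.**

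**Conclusion.** The point holds. Section 4.4.4 contradicts sections 2.0 and 4.3.1 on when the follow-up accelerometer is worn, and no reading of the text reconciles them. The 6-month timing overshoots the anticipated participation by at least 1.2 to 1.5 months and, if followed, would place device-measured activity about 12 to 13 weeks after the other Aim 2 outcomes. The textual conflict needs no assumptions. The duration comparison rests on the stated 7-day wear periods and the anticipated 4 to 5 months. The calendar result holds only if the key dates do. This should be corrected, but it is contained: BMI, the survey outcomes and the number of patients do not change.

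**What to change.** In section 4.4.4, replace the 6-month time point with follow-up 3 months after the clinic visit, in line with sections 4.2.1 and 4.3.1 and with the 3 months in section 2.0. Confirm the change against Figure 2.

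Two additions would help but are not essential: name the 3-month time point for the change-from-baseline analysis in section 5.2, and state that wait-list patients receive PREVENT only after the 7-day follow-up wear has ended.

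The cost is wording only. Section 4.3.1 already schedules the 3-month accelerometer mailing, so no contact, device or patient is added.
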